	
 
Isatuximab: 10 mg/kg weekly for 3 weeks (QW × 3), then every 3 weeks (Q3W) (ie, on Day 1 of each 21-day cycle).
 
					
	REGN2810 (administrated before isatuximab): 350 mg Q3W, (ie, on Day 1 of each 21-day cycle).					
	Dose -1 (may be implemented if 2/6 patients with DLT and then ≥3/12 with DLT or if ≥3/6 patients with DLT at starting dose):					
	
 
Isatuximab: 5 mg/kg QW × 3, then Q3W.
 
					
	REGN2810 (administrated before isatuximab): 350 mg Q3W.					
	Phase 2 part					
	Combination dose for the Phase 2 part will be determined based on safety data from the Phase 1 part. Monotherapy dose for the Phase 2 part will be the isatuximab RP2D.					

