#### 4.3.2 Schedule and dose of administration

REGN2810 is administered as an intravenous (IV) infusion every 3 weeks at 350 mg dose.

A flat IV REGN2810 dose of 350 mg once every 3 weeks (Q3W) was selected, based on population pharmacokinetics (PK) modeling and simulation, as it is expected to provide exposure that closely replicates that observed in patients (mean weight: 80 kg) for the 3 mg/kg Q2W IV regimen in the ongoing first-in-human study R2810-ONC-1423 (NCT02383212). Simulations of REGN2810 exposure in 1000 patients using population PK analyses indicated that:

- A 350 mg Q3W dose in patients resulted in similar (≤20% difference) Ctrough, AUC12 weeks, and Cmax as compared to the 3 mg/kg Q2W dose in the first-in-human patient population (80 kg), and exceeded those observed at the 1 mg/kg Q2W dose.
- The variability in REGN2810 exposure (coefficient of variation) was similar for body-weight adjusted doses as compared to flat doses.

Given the similar predicted exposure for 350 mg Q3W when compared to the 3 mg/kg Q2W regimen, a similar efficacy/safety profile is also expected. Therefore, the 350 mg Q3W IV dose of REGN2810 is being proposed across the REGN2810 program.

In patients with MM, isatuximab exhibits non-linear PK due to the presence of target mediated drug disposition. In addition, tumor burden impacts the PK of isatuximab.

Based on safety, efficacy, PK, and PK/pharmacodynamic analyses, the dose/schedule of isatuximab when used in combination with other therapies for the treatment of MM is 10 mg/kg QW × 4 followed by Q2W. The half-life of isatuximab associated to the linear elimination is 18 days and we hypothesized that the immuno-modulatory mechanisms of isatuximab will be mainly involved in the pharmacological activity of isatuximab; therefore, a less intensive schedule of administration for isatuximab is proposed compared to the schedule used in patients with MMs: 10 mg/kg QW × 3 followed by Q3W. Of note, based on updated pharmacokinetic characterization of isatuximab in 2019, the plasma half-life has been re-estimated to 28 days.

Based on internal safety, efficacy, PK, and PK/pharmacodynamic data analyses, the dose/schedule of isatuximab when used as monotherapy for the treatment of MM is 20 mg/kg QW × 4 followed by Q2W. However, based on the reasons mentioned above and the hypothesis that tumor burden will be lower in patients with prostate cancer compared to MM (ie, less target-mediated drug

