#### 6.6.3 Dose modifications

Guidelines for isatuximab and REGN2810 dose modifications and treatment discontinuation due to hematological and non-hematological adverse reactions in general are outlined in Table 2.

See Section 6.6.4 and Appendix G for guidance for irAEs correlated with REGN2810, and Section 6.6.5 for IARs correlated with isatuximab and REGN2810.

The final decision will be based on the Investigator's judgment, in the best interest of the patient.

11-Jun-2019 Version number: 1

Table 2 - Isatuximab and REGN2810 dose modification guidelines

NCI CTCAE V4.03	management	management	Action and Guidelines
Hematological toxicity			
Grade 1, 2, 3	No change		Patient should be given supportive care and monitored closely.
Grade 3 thrombocytopenia asting >7 days or associated with bleeding	Delay the cycle until bleeding is controlled and platelet >50,000/mm³. Restart treatment with same dose and schedule.		Patient should be given supportive care and monitored closely.
Grade 4	Delay the cycle until ANC >1000/mm³, and platelet >50 000/mm³. Restart with same dose and schedule.  Grade 4 lymphopenia: no change in dose		Permanent discontinuation of study treatment should be considered if toxicity does not resolve within 84 days of last infusion.
Febrile neutropenia and/or neutropenic infection	Delay the cycle until fever and infection recover and ANC >1000/mm³. Restart with same dose and schedule.		
Non-hematological toxicity (other than irAE and IAR)			
Grade 1	No change		N/A
Grade 2 (except alopecia) Grade 3	Delay the cycle until improves to Grade ≤1 or baseline.  Restart treatment at same dose and schedule		It is up to the Investigator's judgment whether to restart the treatment of isatuximab and REGN2810 if the cycle delay is within 14 days.
Grade 4	Permanently discontinue treatment for treatment related AEs		
			If the cycle delay is longer than 14 days, before restarting the treatment, the Investigator must discuss with Sponsor; if it is determined that it is to the best interest of the patient, the treatment may be restarted.  If the cycle delay is longer than 84 days, the treatment must be discontinued.
Immune-related AE: see Table 3 and Appendix G for dose modification and patient management guideline			
Infusion-Associated Reaction: see Table 4 for IAR management guideline			

Abbreviations: AE=adverse event; ANC=absolute neutrophil count; DL-1=dose level minus 1; IAR=infusion-associated reaction; irAE=immune-related adverse event.

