Grade 1 Pneumonitis Interstitial lung disease Acute interstitial pneumonitis	No change in dose	Consider delay or omit dose (see Section 6.6.2). REGN2810 may be continued with close monitoring.	Radiological findings should be followed on serial imaging studies at least every 3 weeks.  Monitor for symptoms every 2 to 3 days.  Consider pulmonary consultation and/or bronchoscopy if clinically indicated.	All attempts should be made to rule out other causes such as metastatic disease, bacterial or viral infection.
Grade 2 Pneumonitis Interstitial lung disease Acute interstitial pneumonitis	Delay or omit dose until resolves to Grade ≤1 (see Section 6.6.2)	Delay or omit dose until resolves to Grade ≤1 (see Section 6.6.2)	To rule out other causes such as infection: Consider pulmonary consultation with bronchoscopy and biopsy/BAL. Consider pulmonary function tests Follow radiological findings on serial imaging studies every 1 to 3 days If the patient is determined to have study treatment-associated pneumonitis Monitor symptoms daily, consider hospitalization Treat with systemic corticosteroids at a dose of 1 to 2 mg/kg/day prednisone or equivalent. When symptoms improve to Grade 1 or less, steroid taper should be started and continued over no less than 4 weeks. Treatment with REGN2810 may be resumed if the event improves to ≤Grade 1 within 12 weeks and corticosteroids have been reduced to the equivalent of methylprednisolone 10 mg by mouth daily or less. Repeat chest imaging monthly as clinically indicated. For Grade 2 pneumonitis that improves to ≤Grade 1 within 12 weeks, the following rules should apply: First episode of pneumonitis: may decrease the dose to 1 mg/kg in subsequent cycles. Second episode of pneumonitis: Discontinue REGN2810 if upon re-challenge the patient develops a second episode of ≤Grade 2 pneumonitis.	All attempts should be made to rule out other causes such as metastatic disease, bacterial or viral infection

Pneumonitis events CTCAE version 4.03 Grade	Isatuximab Dose Management	REGN2810 Dose Management	Actions and Guidelines	Diagnostic considerations

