2.4.4.3 REGN2810 exposure

The REGN2810 exposure will be summarized as follows:

- Total number of cycles started
- Number of cycles started by patient as a continuous variable and by category
- Duration of REGN2810 exposure (weeks) is defined as (Date of the last dose of REGN2810 + 21 days – Date of the first dose of REGN2810)/7
- Actual dose (mg): is defined as actual dose administered
- Cumulative dose (mg): the cumulative dose is the sum of all actual REGN2810 doses
- ADI (mg/week): is defined the cumulative dose (mg) divided by the duration of REGN2810 exposure (weeks)
- RDI (%): $100 \times \frac{\text{ADI (mg/week)}}{\text{Planned Dose Intensity (mg/week)}}$, where the planned dose intensity (mg/week) is 116.7 mg/week for Q3W schedule

The total number of cycles started, number of cycles started by patients as a continuous variable and by category (ie, number [%] of patients receiving at least 1 cycle, at least 2 cycles, etc), duration of REGN2810 exposure, cumulative dose, ADI and RDI will be summarized by descriptive statistics.

The following variables will be derived to describe dose delay and modification:

- Infusion interruption: An infusion will be considered to be interrupted (as collected on eCRF) if the REGN2810 administration is stopped during an infusion before it is completed regardless of whether it is further restarted or not
- Dose omission: a dose is considered omitted if the dose is not administered for the scheduled visit and there are positive dose(s) afterwards

Dose delay and modification will be summarized at the patient and infusion levels as follows:

- Patient level:
 - Number (%) of patients with at least 1 dose omission
 - Number (%) of patients with at least 1 infusion interrupted
 - Number (%) of patients with at least 1 infusion interrupted and re-started
 - Number (%) of patients with at least 1 infusion interrupted and not re-started
- Infusion level:
 - Number of REGN2810 infusions
 - Number (%) of infusions interrupted
 - Number (%) of infusions interrupted and re-started
 - Number (%) of infusions interrupted and not re-started
 - Number (%) of infusions interrupted more than once
 - Number (%) of infusions interrupted at 1st infusion, 2nd infusion, subsequent infusions
 - Time from infusion start to first interruption in minutes summarized as a continuous variable and by category (<5 minutes, 5-10 minutes, etc.)

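### Appendix G Table 19 allows a decrease to 1 mg/kg after a first Grade 2 pneumonitis, a dose this trial defines for neither study drug and one that does not fit flat-dose REGN2810

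*Protocol*

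**What the plan says.** **Table 19 (Appendix G), Grade 2 row.** The dose columns for both drugs say to delay or omit until the event resolves to Grade 1 or less. The action column then gives two rules for an event that improves to that level within 12 weeks. The first, for a first episode, is that sites "may decrease the dose to 1 mg/kg in subsequent cycles". The second is: "Second episode of pneumonitis: Discontinue REGN2810 if upon re-challenge the patient develops a second episode" (of pneumonitis at the grade stated there). Only the second rule names a drug.

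**REGN2810 regimen.** Section 4.3.2 states: "A flat IV REGN2810 dose of 350 mg once every 3 weeks (Q3W) was selected". The dose regimen in the Clinical Trial Summary repeats "REGN2810 (administrated before isatuximab): 350 mg Q3W" for dose level minus 1, and section 6.2.1 also keeps 350 mg at both levels. Section 8.1.2.2 gives 350 mg per administration as the starting dose.

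**Isatuximab regimen.** The levels are 10 mg/kg and, at dose level minus 1, 5 mg/kg. Section 6.3 leaves open a test of 20 mg/kg.

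**General immune-related guidance.** For Grade 2 events, Table 3 (section 6.6.4) offers only delay or omission of REGN2810.

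**Exposure reporting.** Protocol section 13.4.2 lists dose reductions and the reasons for them among the exposure variables for each study drug. SAP sections 2.4.4.2 and 2.4.4.3 derive interruptions and omissions (and, for isatuximab, delays within Cycle 1), but no reductions. SAP section 1.5 declares no modification to the protocol's statistical section.

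**The concern.** A site treating a patient after a first Grade 2 pneumonitis would find a stated option that cannot be matched to the regimen. It gives a weight-based figure where the drug apparently meant has a flat dose, and it does not say which drug is to be changed. Pneumonitis is a serious immune-related event, so an instruction about resuming treatment after it should be usable as written.

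Section 6.6.1 adds weight in two ways. It asks for consultation with the sponsor only when a modification differs from those stated in the protocol, and this one is stated. It also bars a return to the previous dose level once a dose has been decreased, so a patient given the undefined dose would stay below the trial regimen.

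For the analysis, the stake is limited to how such a reduction would be described in the exposure tables.

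**Working it through.** **1. Which drug is meant?** Appendix G is titled for REGN2810 drug-related events. The text just before the disputed sentence concerns resuming REGN2810, and the rule just after it concerns stopping REGN2810. A corticosteroid reading is tempting, because the same cell gives a prednisone dose of 1 to 2 mg/kg/day, but steroids are not dosed by cycle and the paired rule concerns REGN2810. REGN2810 is therefore the likely reading, though the sentence does not say so.

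**2. Does a 1 mg/kg level exist in this trial?**

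| Drug | Levels defined for this trial | 1 mg/kg among them? |
|---|---|---|
| REGN2810 | 350 mg flat, at the starting dose and at dose level minus 1 | No |
| Isatuximab | 10 mg/kg, 5 mg/kg; 20 mg/kg possible | No |

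The protocol mentions 1 mg/kg as a study-drug dose only for other studies: REGN2810 in the first-in-human study (sections 4.3.2 and 4.4.2.2) and isatuximab in a myeloma study (section 4.2.1.1).

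**3. Planned intensity in the SAP.** 350 mg / 3 weeks = 116.67 mg/week. This reproduces the stated "116.7 mg/week for Q3W schedule".

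**4. Size if REGN2810 is meant.** Dose = weight × 1 mg/kg; share = dose / 350 mg.

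- At 80 kg (section 4.3.2, mean weight for the first-in-human study): 80 mg; 80/350 = 22.9%; 1 − 0.229 = 0.771, so 77% lower. If given every 3 weeks, 80/3 = 26.7 mg/week against 116.7.
- At 50 kg (assumed): 50 mg; 50/350 = 14.3%.
- At 120 kg (assumed): 120 mg; 120/350 = 34.3%.
- 1 mg/kg would equal 350 mg only at 350 kg.

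**5. Size if isatuximab is meant.** 1/10 = 10% of the starting dose; 1/5 = 20% of dose level minus 1.

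**6. Where a reduction would show.** SAP section 2.4.4.3 builds cumulative dose, actual dose intensity and relative dose intensity from the dose given, so a reduced REGN2810 dose would lower all three. No SAP variable would count the patient as reduced or give the reason. The all-treated analyses use the dose level received in the first cycle, so a later reduction would not appear in that grouping either.

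**The case against.** The strongest reply is that the wording is permissive, that section 6.6.4 presents Table 3 and Appendix G as guidance to be applied with clinical judgment, and that section 6.6.1 allows dose adjustment for toxicity. A toxicity reduction need not equal a starting dose, and the context makes REGN2810 the probable drug. All of that stands, and it limits the severity. It does not remove the problem: none of these provisions defines a 1 mg/kg level, and section 6.6.1 treats a stated modification as one that needs no consultation.

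Several stronger readings are tempting, but the documents do not support them:

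- **Conflict with Table 2.** A reader might set "Restart treatment at same dose and schedule" against Table 19. That row excludes immune-related events, and Table 2 sends those to Table 3 and Appendix G.
- **Conflict with Table 1.** Table 1 is the Phase 1 cohort de-escalation scheme, not a list of permitted reductions within a patient. Section 6.2.1 is used here only to show which levels the trial defines.
- **A contradiction within the Table 19 row.** Delay or omission applies until recovery, and the disputed sentence applies to later cycles. These are successive steps.
- **Conflict with the SAP's planned intensity.** That figure is simply 350/3 and contradicts nothing.
- **No place for a reduced dose in the exposure analysis.** It would still reach cumulative dose and dose intensity. The missing dose-reduction variable is a separate gap between SAP and protocol, which would exist without Table 19.
- **80 kg as this trial's mean weight.** It describes the first-in-human patients, hence the range above.

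**Conclusion.** The point holds as a minor internal inconsistency. Table 19 states a dose that this trial defines for neither drug, and in a weight-based form that does not match the flat REGN2810 regimen. If REGN2810 is meant, the dose would be 77% below 350 mg at 80 kg, or 14.3% to 34.3% of it over the assumed 50 to 120 kg.

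The option arises only after a first Grade 2 pneumonitis that improves within 12 weeks, and it is optional even then. The number of such events is not given, so the practical effect cannot be sized. Response-rate thresholds, sample size, power and alpha are unaffected.

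The amendment history records that the REGN2810 overdose definition was corrected because it had been expressed by body weight for a flat-dosed drug. That is consistent with Table 19 being a similar leftover, but its origin cannot be established from the documents.

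**What to change.** - **Protocol.** Reconcile the Table 19 sentence with the dose regimen in the Clinical Trial Summary, sections 4.3.2, 6.2.1 and 8.1.2.2, and Table 3 in section 6.6.4. Name the drug concerned. Which dose or rule should apply is for the sponsor to settle; none is proposed here.
- **SAP.** In section 2.4.4, add for each study drug the dose-reduction variable and its reason, as protocol section 13.4.2 lists, or record the omission in section 1.5.

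The cost is a change of protocol wording, a letter to sites and a short SAP addition. Section 6.6.1 already requires changes in study treatment administration to be recorded in the e-CRF.

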#### Appendix H Modification of Diet in Renal Disease (MDRD) equation

Glomerular filtration rate (mL/min/1.73 m^2) =  $175 \times (\text{Serum Creatinine})^{-1.154} \times (\text{Age})^{-0.203} \times (0.742 \text{ if Female}) \times (1.212 \text{ if African-American})$ 

#### Appendix I Multidisciplinary Collegial Meeting Requirement

This appendix provides with country list where the eligibility of patient to take part in the study is to be validated at the multidisciplinary collegial meeting:

France

#### Appendix J PROTOCOL AMENDMENT HISTORY

The Protocol Amendment Summary of Changes Table for the current amendment is located directly before the Table of Contents (TOC).

#### Amendment 1 (05 October 2017)

This amendment is not considered to be substantial based on the criteria set forth in Article 10(a) of Directive 2001/20/EC of the European Parliament and the Council of the European Union.

#### **OVERALL RATIONALE FOR THE AMENDMENT**

The main reason for this amendment was to include a subsection with specific criteria for patients allocated to immunotherapy-based treatment arms to continue treatment through RECIST-defined radiological progression of disease. Other changes were implemented to clarify footnotes in flowcharts for height, weight, and dosing; correct links; add de-escalation text where missing; and delete tables of blood draw volumes because they are provided in the Laboratory Manual.

Section # and Name	Description of Change	Brief Rationale
Clinical Trial Summary,	Administrative and typographical	Correct typographical errors
1.1 Design diagram	changes	and note administrative
1.5.2 For Phase 2 part of Cohort A-2, Stage 2 Phase 2 part of Cohort A-1 and Cohort B (tests for REGN2810 are not applicable for		changes
Cohort A-2, tests for PK are not applicable for cross-over part)		
1.5.3 For Cohort C and Cohort D (tests for REGN2810 are not applicable for Cohort C if isatuximab monotherapy is administered)		
8.3.1 Study treatment		
Appendix A Prostate cancer clinical trials working group 3 criteria for progression		
1.3 Study Flowchart for Phase 1, Phase 2 Cohorts A-1, A-2, B and Cross-over part	Add specific criteria required for patients to continue study treatment after	Per FDA request, to include a subsection with specific criteria

1.4 Study Flowchart for Cohort C and Cohort D

6.5 Retreatment of patientss

	apparent radiographic progression	required for patients allocated to immunotherapy-based treatment arms to continue
6.6.1 General rules		treatment through RECIST-
6.7.1 Duration of study participation for each patient		defined radiological progression
11.1 Permanent treatment discontinuation with IMP product(s)		of disease. References to the subsection were also added in relevant sections.
12.3 Treatment period		reievant sections.

Property of the Sanofi Group - strictly confidential

Section # and Name	Description of Change	Brief Rationale
1.3 Study flowchart for Phase 1, Phase 2 Cohorts A-1, A-2, B and crossover part	Clarify weight/height data collection time point in study flowchart footnote	Ambiguity in flowchart table and footnote may lead to confusion of when to collect height and weight data.
1.4 Study flowchart for Cohort C and Cohort D 1.5.3 For Cohort C and Cohort D (tests for REGN2810 are not applicable for Cohort C if isatuximab monotherapy is administered)	Remove irrelevant/non-applicable text from study flowcharts	Flowcharts in section 1.4 and 1.5.3 are for cohorts without QW dosing, while the footnote included text regarding dose information for QW dosing.
6.2.1 Starting dose and de-escalation design	Add details on dose de-escalation design	Certain description of the dose de-escalation design in Clinical Trial Summary and Design Diagram was not transcribed to Section 6.2.1.

6.5 Retreatment of patients

6.6.3 Dose modifications

6.6.4 General guidelines for the management of immune-related adverse events

	Correct reference to Appendix F to Appendix G	Incorrect hyperlinks in the document led to incorrect appendices referencing.

9.1.5 Immunogenicity

9.2.2 Pharmacokinetic sample handling procedure

9.4 Samples blood volume

	Remove Tables 5, 7, 10, 11	Details on blood draw volumes should be provided to study sites in Laboratory Manual instead of inclusion in the protocol.
9.1.5 Immuogenicity 9.2.3 Bioanalytical methods 9.2.4.1 Noncompartmental analysis 13.1 Determination of sample size Appendix A Prostate cancer clinical trials Working Group 3 criteria for progression Appendix B Response Evaluation Criteria in Solid Tumors version 1.1 Appendix D Modified response evaluation criteria in solid tumors for immune-based therapeutics Appendix G Recommended dose modification or discontinuation and supportive care guidelines for specific REGN2810 drug-related adverse events.	Renumbering of Tables 6-28	Removal of Tables 5, 7, 10, and 11 require renumbering Tables 6-28.

#### Amendment 2 (09 November 2017)

This amendment applied to the UK only and is considered to be substantial based on the criteria set forth in Article 10(a) of Directive 2001/20/EC of the European Parliament and the Council of the European Union.

#### OVERALL RATIONALE FOR THE AMENDMENT

The main reason for this amendment was to clarify that pregnancy testing would be performed on Day 1 of each cycle as required by MRHA regulations.

Section # and Name	Description of Change	Brief Rationale
1.3 Study flowchart for Phase 1, Phase 2 Cohorts Q-1, A-2, B and cross-over part 1.4 Study flowchart for Cohort C and Cohort D 12.3.1 Cycle 1 (Day 1, Day 8 and Day 15) 12.3.2 Subsequent cycles (Day 1) 12.4 End of treatment	Clarify that pregnancy testing must be performed on Day 1 of each cycle prior to the study treatment and at the EOT visit	Per MHRA request, the current protocol is unclear to investigators whether the more frequency tests are a legal requirement or not in the UK according to the phrase "in countries where required by local regulations". In order to meet the legal requirement, MHRA is requesting to indicate that pregnancy testing must be performed on Day 1 of each cycle prior to the study treatment and at the EOT visit.
EOT=end of treatment; MHRA	A= Medicines and Healthcare Products Regulato	ory Agency

